Informed consent for DTM will include a detailed description, in English and Spanish, of the risks and benefits of the study with user-friendly images of the equipment. If the patients decline to participate in DTM, they will continue to receive standard of care and still have surveys administered and data collected over time (as agreed to in consent 1). Based on intention to treat (ITT), they nevertheless will be analyzed as part of the DTM group.

For those patients randomized to DTM, the RN will explain to the patients that if they agree to participate, they will be asked to measure vital signs daily, receive weekly telehealth “visits” with the telehealth RN (with appropriate assurances regarding confidentiality), and receive reminders of their weekly visits. The experienced bilingual RN will be trained in the proper recruitment of patients to eliminate selection bias based on a standardized protocol. The research RN will also explain to the DTM patient that s/he will have a bilingual trainer meet them at their home and that they will receive training on how to properly use the equipment.

For those patients randomized to COM, the research RN will have monthly phone contacts to determine how the patient is doing, how many days during the week they have been sick, and whether they have been to an unscheduled doctors visit, the ED or hospital during the last month and how many days they have been sick. Lastly, in both groups, the enroller will let patients know that they will be asked to complete pre and post surveys. The enroller will be trained on the proposed enrollment practices to ensure objective, unbiased and systematic selection and recruitment of participants.

DTM patients will be asked if they prefer to involve their caregiver; if patients agree, caregivers will be provided with the caregiver app (Figure 3). The bilingual enroller will explain to DTM patients that they will provide DTM training at their home.

We propose to study H/L patients with T2D, recruited from the Ambulatory Care Unit at LIJMC and the Division of General Internal Medicine Practice located in Queens NY, one of the most diverse populations in the world. We also propose to recruit at Southside Hospital. NUMC and Glen Cove Hospital as well as the Dolan Family Health Center. We selected these sites because 1) clinic patient statistics meet our enrollment criteria, with 4,092 adults H/L patients with T2D (well over the

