**Figure 1. Conceptual Model of Diabetes Telehealth Management**

**Comparators: 1. Intervention: Diabetes Telehealth Management (DTM),** based on the 2018 ADA Standards for T2D, uses smart devices to share information

[figure not shown]
Measures	DTM	COM
Diabetes Quality of Life	Months 1, 6	Months 1, 6
HbA1C (Primary Outcome Variable)	Months 1, 3, 6	Months 1,3, 6
Medication Adherence	Months 1,6	Months 1,6
Diabetes Management Self-Efficacy	Months 1,6	Months 1,6
Diabetes Distress	Months 1,6	Months 1,6
Problem Areas in Diabetes Questionnaire	Months 1,6	Months 1,6
Patient Engagement	Months 1,6	Months 1,6
Telehealth Satisfaction and Usefulness Questionnaire	Month 6	None
Medical Outcomes Study (MOS) Social Support Survey	Months 1,6	Months 1,6
Unscheduled T2D sick visits & number of sick days	Weekly	Monthly
Lipid profile	Months 1,3,6	Months 1, 3,6
Weight	Daily	Every 3 months
Blood pressure	Daily	Every 3 months
Glucose Levels	Daily/MD Advise	Daily/MD Advise
Inpatient Utilization	Daily	Every 3 months
Hypoglycemia Episodes (blood glucose <70)	Weekly	Every 3 months
Comparator Components	DTM	COM
Based on 2018 ADA Standards	Yes	Yes
Real time informative clinician patient video interaction with frequent feedback	Yes	No
Vital signs discussion	Weekly	Every 3 months
Diabetes management discussion	Weekly	Every 3 months
Timely transmission and remote interpretation of patient data	Yes	No
Telehealth nurse visit	Yes	No
Comprehensive health assessment	Yes	Yes
Diabetes management education with interactive quizzes and clinician feedback	Yes	No
Caregiver involvement through caregiver app	Yes	No

between patients, caregivers, and clinicians. DTM has 7 components that differentiate it from COM (Table 1): **1) real time informative clinician patient video interaction; 2) frequent vital signs discussion; 3) frequent diabetes management discussion; 4) timely vital signs/physiological data transmission/interpretation (e.g., GM, automatically transmitted and reviewed by the clinician daily); 5) a weekly “virtual” visit, wherein clinicians can “re-check” vitals, and discuss prior week’s data in relation to medication, nutrition, and exercise, further involving**

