- d) ***Exit quality interviews:*** *Patients and caregivers in the DTM arm who complete the 6-month intervention or drop out of the CER RCT study will be asked to provide feedback on their experiences. The caregiver will not be consented to take part in the qualitative exit interviews, but will receive an information sheet that will detail what we will ask them.*
- e) ***Caregiver usability app and engagement:*** *We will assess engagement as number of minutes/day spent on the smart device and number of minutes/each component of the app (e.g., educational videos).*

*Our Community Advisory Board (CAB) consists of the study team, community members, health care practitioners, health policy experts, subject matter experts, patient advisory committee and provider panel. Throughout this study, the CAB will be meeting 9 times, however, only three of those times we will be conducting focus groups. Our first CAB meeting will be a focus group (pre-pilot). During this time, the CAB will be broken down into three groups, each of which will participate in a focus group: 1. The Main CAB focus group, which will include all participants. After conducting the Main CAB focus group, the CAB will separate into two groups. 2. The Patient Advisory Committee (PAC) Focus Group and 3) The Provider Focus Group. This CAB meeting will be to discuss adaptation to outcomes, intervention and study design. Participants will be consented to be in the Focus Groups and then consented to be audio recorded.*

*We will implement the recommendations from the CAB and then conduct a pilot study. After the pilot study, we will conduct our Third CAB meeting to discuss adaptations to outcomes, intervention and study design. See table below for further information:*

Name	Description and Additional Information
1. CAB Focus Group # 1 (preliminary pre-pilot)	Focus groups with CAB to discuss adaptations to outcomes, intervention and study design.
a. PAC Focus Group (pre-pilot)	Focus group with PAC members to discuss adaptations to outcomes, intervention and study design
b. Provider Focus Groups (pre-pilot)	Provider focus group to tailor the intervention from the provider perspective
2. CAB focus group # 2 (pre-pilot)	Preliminary Adaptions combining CAB & PAC guidance presented to CAB. Provide summary of findings to PCORI.
a. PAC Focus Group (pre-pilot)	Focus group with PAC members to discuss adaptations to outcomes, intervention and study design

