transformations will be considered for all analyses. Subgroup analyses are outlined separately below. **Assess data source adequacy.** Given the RCT approach, it is unlikely that demographics will be misrepresented in treatment groups. Thus, confounding is highly unlikely. However, demographic variables such as age, race/ethnicity, and insurance will be easy to measure through self-report, based on the success of an ongoing PCORI trial of telehealth-delivered CHF management (PI: [name]). These data will be a combination of self-report/medical record verification. The primary endpoint, HbA1c, is highly reliable as it is derived from a reputable, licensed laboratory. **Planned sensitivity analyses to determine the impact of key assumptions.** For all analyses, underlying assumptions will be evaluated using SAS diagnostic tools (PROC GENMOD, PROC MIXED, and PROC GLM). **Address missing data.** The best protection against missing data is to prevent it in the first place. To this end: 1) we have already partnered with the clinic directors to ensure that patient records will be available; 2) two separate team members, [name] and [name], will track the completion of data weekly (checking each other's data), which will be reported at weekly research meetings; and 3) each team member will have clearly defined tasks and will regularly report on progress. **Prevention and monitoring of missing data on outcomes:** Participants in both arms will be contacted (DTM through video visit; COM monthly by phone). This will be a "check-in" contact to assess how patients are doing and whether they have interacted with the healthcare system (i.e., ED visits). The RN will make all patient contact. If a patient does not continue with the study, we will ask for the reason for discontinuance. We will ask permission to collect outcome data as scheduled. We believe that this will help obtain outcome data in the spirit of ITT. In addition, we will use our pilot study and focus groups or structured interviews to identify potential challenges to data collection that we can address a priori. During data collection researchers Dr (s) [name] and [name] will assess weekly capture of all outcomes. The database management system, managed by the Biostatistics Unit, includes features that report test and form completion. The study team will monitor data collection and troubleshoot during regular meetings. We will also minimize risk of incomplete data by making surveys as easy as possible for the patient, conducted in their home; we will also perform cognitive pretesting with our PAC and field test surveys with pilot patients. **Statistical methods to handle missing data.** We will use standard methods of multiple imputation. Since HbA1c will be measured 4 times (baseline, 3 months 6 months and 12 months) pre-HbA1c data will necessarily be available and 3 or 6-month data (theoretically) will not. Therefore, a monotone missing data structure will be used. The missing data mechanism will be assumed to be missing at random (MAR). Similar approaches will be used for secondary outcomes-continuous and binary. **Recording and reporting reasons for dropout and missing data, and account for all patients in reports.** We will use the CONSORT diagram method to describe/account for subjects who drop out or for whom outcome variables are missing. Tables will reflect frequency/reasons for missing data. **Sensitivity of inferences to missing data methods and assumptions, and incorporation into interpretation.** A commonly used sensitivity analysis for the MAR assumption in multiple imputation is based on the pattern mixture model approach, modeling distribution of responses as a mixture of observed responses and missing responses. **Goals of planned HTE analyses.** We will evaluate whether the treatment effect in H/L patients with a caregiver participating differs from those that do not by examining the treatment x caregiver status interaction term. Similarly, we will also evaluate whether the treatment effect in female H/L patients differs from male patients by examining the treatment x gender interaction term. It should be emphasized, however, given our resources, there may be insufficient power to detect such interactions. Therefore, these analyses will be exploratory. If feasible, we will also evaluate the treatment x SE interaction. **HTE analysis plan.** In keeping with ICH E9 statistical principles for clinical trials (V.7G), the interaction terms for treatment x caregiver status, and treatment x gender will be included in the primary analysis, as well as main effects for treatment, caregiver, and gender. We plan on exploratory subgroup analyses to explore differential effects of treatment on caregiver

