
and gender groups. Upon finding a significant treatment x caregiver interaction (or treatment x gender interaction), the effect of treatment on A1C will be estimated separately for caregiver status (Y/N) (likewise for gender). Estimate of treatment effects and their 95% CI will be constructed. **The basis for all HTE claims based on appropriate statistical contrasts among groups being compared.** The literature and discussions with our CAB indicate the importance of family in the H/L culture. Given the different social/familial roles of women, we will also explore potential gender differences. We will also look at type of caregiver (paid/family) and explore caregiver type in a post hoc analysis to better understand the effect of caregiving. **HTE analysis plan to report all pre-specified analyses and, at minimum, the number of post-hoc analyses, including all subgroups and outcomes analyzed.** With the rich data set expected from this study, we will examine data patterns in an exploratory post-hoc way to identify potential trends not specified a priori. While we will use both exploratory and standard statistical approaches, p values, and associated CIs will be interpreted cautiously, as firm conclusions cannot be drawn. Post-hoc analyses will be adjusted for multiple testing. **Reporting plan to allow for assessments of the study's internal and external validity.** We will report trial results according to the CONSORT guidelines for reporting of RCTs, using the CONSORT 2010 checklist. We will report the progression of patients through the study using the CONSORT flow diagram, showing numbers of patients at each study point (enrollment, allocation, follow-up), and reasons for attrition at each point. For reporting qualitative results, we will use the COREQ a 32-item checklist for interviews/focus groups.

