Patient contact information will be collected in secure electronic documents only accessible to the PI and study team. For the focus groups, which will be audio recorded, participants will give informed consent for participation and separate consent to be audiotaped. **Subjects who signed consent for the pilot study and focus group, but will now participate in a structured phone interview instead of focus group, we are seeking a waiver of documentation of consent and HIPAA authorization. We will read the script approved by IRB to get the subjects' authorization. The subjects will be informed of the change over the phone and also asked for their authorization to be audio recorded before the interview begins.**

With current COVID\_19 pandemic, the team also requests waiver of documentation of HIPAA authorization, as the interview is minimal risk, the interviewees are not readily available in person (and are not expected to be in the near future), and it would be reasonably expected that the response rate to a mailed HIPAA authorization would be so low that the research would be impracticable to perform. The research could likewise not be performed without use of PHI, as the interviews will discuss patient health status and will be audio recorded.

*In our main RCT study, for patients in the telemonitoring arm, the patient will be consenting that we can contact their caregiver. We will ask the patient whether or not they have a caregiver and if they will give the caregiver permission to see their daily vital signs during the study. At this point there will be verbal consent on the part of the patient that we may contact the caregiver, and the team member, who is consenting, will be indicating on the enrollment note that verbal consent was given by the patient. Once consent is given by the patient, we will provide the caregiver with an information sheet outlining what our study entails (see information sheet attached).*

*Our Research Nurse and Recruitment specialist are both fluent in Spanish. During the recruitment and consenting process, our research team will ask the patient what is their preferred language (either English or Spanish) for which they would like to be consented. All consent forms will be translated into Spanish.*

*In the state of NY, any participants under the age of 18 are considered children. If your study involves children, additional information should be provided to describe:*

- *How parental permission will be obtained*

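### Caregiver status is undefined in COM and set by patient choice after allocation in DTM, so the treatment × caregiver term in the primary model is either not estimable or describes DTM with the app bundled in

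*Combined protocol and SAP*

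**What the plan says.** - **Subgroup.** Section 7 (Participant subgroups) bases the Yes/No caregiver subgroups on whether a caregiver takes part. Section 12 (Goals of planned HTE analyses) says the same: "We will evaluate whether the treatment effect in H/L patients with a caregiver participating differs from those that do not".
- **Model.** Section 12 (Primary Analysis for Aim 2) adjusts HbA1c change for caregiver status, treats it as a stratification variable, and includes its main effect and its interaction with treatment. A significant interaction leads to separate treatment effects by caregiver status. The HTE analysis plan repeats that the interaction belongs to the primary analysis.
- **How a caregiver joins.** Section 6: "DTM patients will be asked if they prefer to involve their caregiver; if patients agree, caregivers will be provided with the caregiver app". Section 23: "for patients in the telemonitoring arm, the patient will be consenting that we can contact their caregiver", followed by "We will ask the patient whether or not they have a caregiver" in the same DTM paragraph, which goes on to permission to see daily vital signs.
- **Status of the app.** In the comparator table in Section 11, "Caregiver involvement through caregiver app" is Yes for DTM and No for COM. The text lists the app as the seventh of seven components that set DTM apart.
- **Allocation.** Section 6 has the recruiter obtain a randomisation number after the first consent. It mentions neither stratification nor recording of caregiver status before that point.
- **Caveats.** Section 12 calls the subgroup analyses exploratory because power may be insufficient, and urges caution over post-hoc p-values. A separate post-hoc look at paid versus family caregivers is meant to "explore caregiver type in a post hoc analysis to better understand the effect of caregiving".

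**The concern.** An interaction between treatment and a patient characteristic needs that characteristic to be defined in both arms, preferably before randomisation. Here the characteristic is described as taking part through something only one arm is offered, and it is settled after allocation by the DTM patient.

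Two things are at stake. The first is the primary analysis: these terms sit in the model for the primary endpoint, so a poor definition can change what the treatment coefficient means. The second is interpretation: if the interaction is significant, the plan reports separate effects with and without a caregiver. Readers could take these as evidence that caregivers change the effect of DTM, when they may reflect the app or, under one definition, simply who opted in.

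**Working it through.** **Inputs.** From Section 12, Sample Size Justification: SD of 6-month HbA1c change 1.2%, 112 per group, two-sided 5% level, 80% power, difference stated as 0.5% and then as 0.45%. From Section 12, caregiver app utilisation: at least 50% of patients expected to have a participating caregiver; I use 50%, with 30% and 70% as a range.

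**1. The plan's own figure.** n per group = 2(1.96 + 0.84)² × SD² / difference². With 0.45% this gives 112 and power 80.1%, so the stated size reproduces. With 0.5% it gives 91. I use 0.45% below. The plan gives no figure for the interaction.

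**2. Definition A: status = caregiver participating.** Write the model as b0 + b1·T + b2·C + b3·T·C, with T = 1 for DTM and C = 1 for Yes. No COM patient can be Yes, so C = 0 whenever T = 0, and T·C = C for everyone. The four-column design matrix has rank 3. Only b2 + b3 is estimable, and it equals mean(DTM with app) − mean(DTM without app). With No as reference, b1 equals mean(DTM without app) − mean(all COM).

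An illustration with assumed values: DTM lowers HbA1c by 0.30% in everyone, the app adds nothing, and patients with caregivers do 0.20% better in either arm. Half have caregivers.

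| | Caregiver | No caregiver |
|---|---|---|
| DTM | −0.50% | −0.30% |
| COM | −0.20% | 0.00% |

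- True interaction: (−0.50 + 0.20) − (−0.30 − 0.00) = 0.00%.
- What Definition A reports as the caregiver contrast: −0.50 + 0.30 = −0.20%, a false sign of modification.
- Randomised contrast: (−0.50 − 0.30)/2 − (−0.20 + 0.00)/2 = −0.40 + 0.10 = −0.30%.
- b1 under Definition A: −0.30 − (−0.10) = −0.20%, which is not the randomised contrast.

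**3. Definition B: status = willing caregiver available, recorded before randomisation in both arms.** The matrix has rank 4. In the same illustration the interaction is 0.00%, as it should be, so the opt-in bias is gone. For precision, with proportion p having a caregiver:

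SE = 1.2 × √2 × √[1/(112p) + 1/(112(1 − p))]

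- p = 50%: 1.2 × √(4/56) = 0.32%. Interaction detectable with 80% power: 2.80 × 0.32 ≈ 0.90%. Power for a 0.45% interaction: 29%.
- p = 30% or 70%: SE 0.35%, detectable 0.98%, power 25%.

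**4. What Definition B still cannot separate.** Keep the −0.30% core effect, drop the prognostic difference, and suppose every DTM patient with a caregiver receives the app. If the app adds −0.30% and having a caregiver modifies nothing, the DTM means are −0.60% and −0.30% and both COM means are 0.00%. If the app adds nothing and patients with caregivers respond 0.30% better, all four means are the same. The interaction is −0.30% either way, and no sample size tells the two apart.

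**The case against.** **The primary-analysis text calls caregiver status a stratification variable.** That suggests a baseline variable known in both arms, and on that reading the interaction is a sound difference between two randomised DTM-versus-COM contrasts. This stands as a possible reading. However, Section 6 describes no stratification or baseline recording, and Sections 7 and 12 define the subgroup by participation. The social support survey is given in both arms and is filed under caregiver support in Table 2, but it is a multi-item support scale, not a Yes/No caregiver status.

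**DTM is a package, and the app is of use only to patients with a caregiver.** On this view the plan never promised to separate the two. That largely stands: bundling limits interpretation and does not invalidate a baseline-defined interaction. A reader might infer that the interaction compares two versions of DTM whatever the definition and can show nothing about caregivers. The documents do not support that, since it holds only if COM patients are all coded No.

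**The analyses are already labelled exploratory.** True, and it limits the severity. But the stated reasons are power and post-hoc testing, not the missing COM definition, and the terms remain in the primary model.

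**The phrase about the effect of caregiving belongs to the paid/family analysis.** This stands. A reader might infer that the plan reads the interaction itself that way, but the text does not say so. Nor does it say that a significant interaction will be reported as caregivers improving DTM.

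**The app is not the caregivers' only activity.** Exit interviews cover "Patients and caregivers in the DTM arm who complete the 6-month intervention" and those who drop out, and caregivers also give usability ratings. Neither supplies a counterpart in COM.

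**Conclusion.** The point holds in conditional form. The readable text does not define caregiver status for COM patients, and in DTM it is settled after allocation by patient choice. Read literally, the interaction is aliased with the caregiver main effect, and with No as reference the treatment coefficient departs from the randomised contrast (−0.20% instead of −0.30% in the illustration). With a baseline definition in both arms, the interaction is valid for the DTM package as a whole, with a standard error of about 0.32% HbA1c. It still cannot attribute a difference to the caregiver apart from the app.

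The 0.32% assumes SD 1.2%, 112 analysed per arm, half with a caregiver, and no precision gain from baseline adjustment. It applies only to the baseline definition. The cell means are illustrative, not predictions. This should be corrected before analysis; the exploratory label keeps it from being more serious.

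**What to change.** 1. In Section 12 (Primary Analysis, Goals of planned HTE analyses, HTE analysis plan), define caregiver status as availability and willingness of a caregiver, recorded before randomisation in both arms. Use that variable in the model, whether or not the app is later taken up. Because the first consent withholds the full study description, the question can be worded without mentioning the app.
2. Compare each DTM stratum with the COM patients of the same baseline status, with 95% confidence intervals.
3. State that any interaction is heterogeneity of the DTM package, app included for those with a caregiver, and not evidence of a caregiver effect apart from the app.
4. If status was not recorded in COM before allocation, remove the caregiver main effect and interaction from the primary model. Report DTM with versus without the app as a non-randomised, descriptive comparison within DTM.
5. Describe the paid/family comparison as descriptive.

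The cost is one extra baseline item and some rewording. The plan also gives up a caregiver-moderation claim that its design cannot support.
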